12.1. DERIVATIONS

The following variables will be derived:

- Age (years) = integer [(Date of informed consent – “15/Jul/year of birth”) / 365.25]
- Time from first diagnosis of melanoma to study enrolment (months) = [(Date of informed consent – date of first diagnosis of melanoma)/30.4]
If Date of first diagnosis of melanoma is partial, the following conventions will be used:
 - If day is unknown, but month and year are known, use first day of the month;
 - If day and month are unknown, but year is known, use 01 January;
 - If day, month and year are unknown, leave it missing.
- Time from first recurrence/relapse to study enrolment (months) = [(Date of informed consent – date of first recurrence/relapse)/30.4]
If Date of first recurrence/relapse is partial, the following conventions will be used:
 - If day is unknown, but month and year are known, use 15 as day;
 - If day and month are unknown, but year is known, use 01 July;
 - If day, month and year are unknown, leave it missing.
- Time from most recent recurrence/relapse to study enrolment (months) = [(Date of informed consent – date of most recent recurrence/relapse)/30.4]
If Date of most recent recurrence/relapse is partial, the following conventions will be used:
 - If day is unknown, but month and year are known, use 15 as day;
 - If day and month are unknown, but year is known, use 01 July;
 - If day, month and year are unknown, leave it missing.

13. MEDICAL HISTORY

Medical history information will be presented for the ITT set.

Medical history verbatims will be coded using MedDRA dictionary version 20.0 or higher.

Medical conditions with “Ongoing” field not ticked in eCRF will be considered as previous diseases while those reported as “Ongoing” in eCRF will be considered as concomitant diseases.

Previous and concomitant diseases will be analyzed separately with frequency tables reporting the number of patients who exhibited at least one disease and showing diseases by primary System Organ Class and Preferred Term by treatment arm.

Line listings of previous and concomitant diseases will be produced for the ITT set.

14. PHYSICAL EXAMINATION

Physical examination information will be presented for the ITT set.

Physical examination verbatims will be derived from the eCRF “Physical Examination” form in the “If abnormal, specify” field and will be coded using MedDRA dictionary version 20.0 or higher.

Clinically significant and not clinically significant abnormalities will be analyzed separately with frequency tables reporting the number of patients who exhibited at least one abnormality and showing abnormalities by primary System Organ Class and Preferred Term by treatment arm.

A line listing of physical examinations and significant abnormalities will be produced for the ITT set.

15. SYSTEMIC ADJUVANT TREATMENTS

Systemic adjuvant treatments will be presented for the ITT set and coded using WHO-DRL dictionary version 2017 or higher.

Prior systemic treatments are those treatments with “Ongoing” field not ticked and which stopped prior to the first dose of study medication.

Concomitant systemic treatments are those reported as “Ongoing” in the “Prior systemic treatment” eCRF form.

Frequency tables of prior and concomitant systemic treatments by primary therapeutic subgroup (3rd level ATC level subgroup) and generic name will be presented by treatment arm.

Line listings of prior and concomitant systemic treatments will be produced.

16. PRIOR RADIATION TREATMENTS

Prior radiation treatments will be presented for the ITT set and coded using WHO-DRL dictionary version 2017 or higher.

A frequency table of prior radiation treatments by primary therapeutic subgroup (3rd level ATC level subgroup) and generic name will be presented by treatment arm.

A line listing will be produced for the ITT set.

17. PRIOR MELANOMA-RELATED SURGERY

Prior (melanoma-related) surgeries will be presented for the ITT set and coded using WHO-DRL dictionary version 2017 or higher.

A frequency table of prior surgeries by primary therapeutic subgroup (3rd level ATC level subgroup) and generic name will be presented by treatment arm.

A line listing will be produced for the ITT set.

18. MEDICATIONS

Medications will be presented for the ITT set and coded using WHO-DRL dictionary version 2017 or higher.

Prior medications are those which stopped prior to the first dose of study medication.

Concomitant medications are those which:

- Started prior to, on or after the first dose of study medication and started no later than date of last study dose,
- AND ended on or after the date of first dose of study medication or were ongoing at the date of last study dose.
- If the date of last study dose is unknown the medication will be considered as concomitant.

Also, see [Table 9](#) for handling of partial dates for medications, in the case where it is not possible to define a medication as prior or concomitant, the medication will be classified by the worst case.

The following tables will be presented:

- A frequency tables of prior medications by primary therapeutic subgroup (3rd level ATC level subgroup) and generic name by treatment arm.
- A frequency tables of concomitant medications by primary therapeutic subgroup (3rd level ATC level subgroup) and generic name by treatment arm.

Data listings of prior and concomitant medications will be produced.

19. STUDY MEDICATION EXPOSURE AND COMPLIANCE

Exposure in days and compliance to oral IMPs (LGX818 and MEK162) will be presented for the SAF set. The date of first study drug administration will be taken from the eCRF “LGX818 (450 mg p.o od)”, “MEK162 (45 mg p.o. bid)”, “Nivolumab 1 mg/kg solution IV”, “Ipilimumab 3 mg/kg solution IV” taking the “Start therapy date” which occurs first.

The date of last dose of study medication will be taken from the eCRF “End of Treatment” form (“Date when the investigational product was last taken”). If this date is missing, the date of last study medication will be taken from the eCRF “LGX818 (450 mg p.o od)”, “MEK162 (45 mg p.o. bid)”, “Nivolumab 1 mg/kg solution IV”, “Ipilimumab 3 mg/kg solution IV” taking the “End therapy date” which occurs last.

Temporarily interruptions and dose changes are not considered for overall duration of exposure.

Default summary statistics will be presented for overall duration of exposure and duration of exposure to each study drug by treatment arm (see specifications for derivations in [Section 19.1](#)). A line listing of duration of exposure will be produced.

Compliance to oral IMPs (LGX818 and MEK162) will be summarized with default statistics by treatment arm. A line listing will be produced.

19.1. DERIVATIONS

Overall duration of exposure [weeks]: $[(\text{date of last dose} - \text{date of first study drug administration} + 1) / 7]$.

Duration of exposure to LGX818 [weeks]: sum over all cycles $[(\text{end therapy date} - \text{start therapy date} + 1) / 7]$.

Duration of exposure to MEK162 [weeks]: sum over all cycles $[(\text{end therapy date} - \text{start therapy date} + 1) / 7]$.

Duration of exposure to Nivolumab [weeks]: sum over all cycles $[(\text{end therapy date} - \text{start therapy date} + 1) / 7]$. For this calculation consider study periods with 1 mg/kg and 3 mg/kg IV infusion.

Duration of exposure to Ipilimumab [weeks]: sum over all cycles $[(\text{end therapy date} - \text{start therapy date} + 1) / 7]$.

Compliance to LGX818 [%] = Total dose administered of LGX818 over all cycles / (Total daily dose to be administered as per protocol x duration of exposure to LGX818 [days]) x 100. Note that total daily dose to be administered as per protocol is 450 mg.

Compliance to MEK162 [%] = Total dose administered of MEK162 over all cycles / (Total daily dose to be administered as per protocol x duration of exposure to MEK162 [days]) x 100. Note that total daily dose to be administered as per protocol is 90 mg.

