6. MAJOR PROTOCOL DEVIATIONS

Major protocol deviations are protocol deviations that might significantly affect the completeness, accuracy, and/or reliability of the study data or that might significantly affect a subject's rights, safety, or well-being.

Major protocol deviations include:

- Any violations of Inclusion and/or Exclusion criteria;
- Incorrect dose of investigational product taken (Dose reduced/Dose delayed/Dose delayed and reduced) for more than 3 consecutive IMP cycles;
- Repeated or severe non-compliance to intake of investigational product (less than 80% or more than 120% of the prescribed dose of LGX818 and MEK162);
- Treatment with any other investigational agent at any time during the study;
- Randomized patient who received an incorrect treatment

The above major protocol deviations will be identified and confirmed prior to or at the Data Review Meeting at the latest and they will lead to the exclusion of a subject from the PP set.

Additional major protocol violations will be identified and documented following a data review meeting prior to database lock.

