XXX	XXX	XXXXXXXXXX	XXX	XXX	XXX	DDMMYYYY	XXX	XXX	XXX	XXX
XXX	XXX	XXXXXXXXXX	XXX	XXX	XXX	DDMMYYYY	XXX	XXX	XXX	XXX
XXX	XXX	XXXXXXXXXX	XXX	XXX	XXX	DDMMYYYY	XXX	XXX	XXX	XXX
XXX	XXX	XXXXXXXXXX	XXX	XXX	XXX	DDMMYYYY	XXX	XXX	XXX	XXX

Source: XXXX.SAS, Run on DDMMYYYY

Listing 42) Administration with Investigational Products

POPULATION: ITT

Treatment Arm	Site	Patient Number	Visit	IMP	IMP administered ?	If not, reason	Date of dispensation (DDMMYYYY)	Start therapy date (DDMMYYYY)	End therapy date (DDMMYYYY)	Dose	Unit	Administration	Reason for reduction/delay/definite interruption	Reduced dose
XXX	XXX	XXXXXXXX X	XXX	XXX	XXX	XXX	DDMMYYYY	DDMMYYYY	DDMMYYYY	XXX	XXX	XXX	XXX	XXX
				XXX	XXX	XXX	DDMMYYYY	DDMMYYYY	DDMMYYYY	XXX	XXX	XXX	XXX	XXX
				XXX	XXX	XXX	DDMMYYYY	DDMMYYYY	DDMMYYYY	XXX	XXX	XXX	XXX	XXX
				XXX	XXX	XXX	DDMMYYYY	DDMMYYYY	DDMMYYYY	XXX	XXX	XXX	XXX	XXX
				XXX	XXX	XXX	DDMMYYYY	DDMMYYYY	DDMMYYYY	XXX	XXX	XXX	XXX	XXX
XXX	XXX	XXXXXXXX X	XXX	XXX	XXX	DDMMYYYY	DDMMYYYY	DDMMYYYY	XXX	XXX	XXX	XXX	XXX	
XXX	XXX	XXXXXXXX X	XXX	XXX	XXX	DDMMYYYY	DDMMYYYY	DDMMYYYY	XXX	XXX	XXX	XXX	XXX	

Source: XXXX.SAS, Run on DDMMYYYY

Listing 43) LGX818

POPULATION: ITT

Trt Arm	Site	Pt Nr.	Visit	Date of dispensation (DDMMYYYY)	Batch #1 (50 mg)	Batch #2 (100 mg)	Batch #3 (100 mg)	Batch #4 (100 mg)	Batch #5 (100 mg)	Dose	Taken correctly?	If not, reason	Nr. of capsules returned
XXX	XXX	XXXXXXXX	XXX	DDMMYYYY	XXX	XXX	XXX	XXX	XXX	XXX	XXX	XXX	XXX
				DDMMYYYY	XXX	XXX	XXX	XXX	XXX	XXX	XXX	XXX	XXX
			XXX	DDMMYYYY	XXX	XXX	XXX	XXX	XXX	XXX	XXX	XXX	XXX
				DDMMYYYY	XXX	XXX	XXX	XXX	XXX	XXX	XXX	XXX	XXX
			XXX	DDMMYYYY	XXX	XXX	XXX	XXX	XXX	XXX	XXX	XXX	XXX
				DDMMYYYY	XXX	XXX	XXX	XXX	XXX	XXX	XXX	XXX	XXX
XXX	XXX	XXXXXXXX	XXX	DDMMYYYY	XXX	XXX	XXX	XXX	XXX	XXX	XXX	XXX	XXX
XXX	XXX	XXXXXXXX	XXX	DDMMYYYY	XXX	XXX	XXX	XXX	XXX	XXX	XXX	XXX	XXX

Source: XXXX.SAS, Run on DDMMYYYY

Listing 44) MEK162

POPULATION: ITT

Trt Arm	Site	Pt Nr.	Visit	Date of dispensation (DDMMYYYY)	Batch #1 (15 mg)	Batch #2 (15 mg)	Batch #3 (15 mg)	Total Daily Dose	Taken correctly?	If not, reason	Nr. of capsules returned	Diary completed correctly and returned?
XXX	XXX	XXXXXXXX	XXX	DDMMYYYY	XXX	XXX	XXX	XXX	XXX	XXX	XXX	XXX
				DDMMYYYY	XXX	XXX	XXX	XXX	XXX	XXX	XXX	XXX
			XXX	DDMMYYYY	XXX	XXX	XXX	XXX	XXX	XXX	XXX	XXX
				DDMMYYYY	XXX	XXX	XXX	XXX	XXX	XXX	XXX	XXX
			XXX	DDMMYYYY	XXX	XXX	XXX	XXX	XXX	XXX	XXX	XXX
				DDMMYYYY	XXX	XXX	XXX	XXX	XXX	XXX	XXX	XXX
XXX	XXX	XXXXXXXX	XXX	DDMMYYYY	XXX	XXX	XXX	XXX	XXX	XXX	XXX	XXX

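### Section 19.1 measures compliance against the fixed full protocol dose, while the section 6 per-protocol rule is set against the prescribed dose; the two need reconciling

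*Supplement*

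**What the plan says.** SAP section 19.1 defines compliance for each oral drug as total dose taken over all cycles, divided by the protocol daily dose times days of exposure, times 100. The numerator is "Total dose administered of LGX818 over all cycles" and its MEK162 counterpart. The daily dose in the denominator is a constant: "Note that total daily dose to be administered as per protocol is 450 mg" for LGX818 and "Note that total daily dose to be administered as per protocol is 90 mg" for MEK162. Days come from the exposure derivation ("Duration of exposure to LGX818 [weeks]: sum over all cycles", end date minus start date plus one). Nothing in the formula changes when the dose is reduced. Section 19 says that the result is summarised by arm and listed.

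Section 6 lists the major deviations that lead to exclusion from the PP set. One is "Repeated or severe non-compliance to intake of investigational product", bracketed as "less than 80% or more than 120% of the prescribed dose of LGX818 and MEK162". Another is "Incorrect dose of investigational product taken (Dose reduced/Dose delayed/Dose delayed and reduced) for more than 3 consecutive IMP cycles". Deviations are to be confirmed at the Data Review Meeting at the latest, and section 7 has set membership agreed case by case. Section 7 also says that the primary variable, OS, is analysed again in the PP set.

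The plan expects dose reductions and records them. Section 6 names them, and Listing 42 has a dose field, a column headed "Reason for reduction/delay/definite interruption" and a reduced-dose field.

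**The concern.** There are two denominators for what looks like one percentage. Dose taken over dose prescribed says whether the patient followed instructions. Dose taken over full protocol dose says how much of the planned treatment was delivered, which is relative dose intensity. The two agree only while the patient is prescribed full dose.

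Two things are at stake. Table 24 would present dose reductions as reduced compliance, and this follows from the formula alone. In addition, if the section 19.1 percentage is used to apply the section 6 limits, membership of the PP set could be wrong in both directions: some adherent patients on a reduced dose would be flagged, and some who took more than a reduced prescription would not.

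**Working it through.** **Inputs.** The regimen in section 4.3 is LGX818 450 mg once daily and MEK162 45 mg twice daily. The limits of 80% and 120% are from section 6. The documents give no reduction steps, so the reduced levels below are assumptions chosen to fit the unit strengths in Listings 43 and 44 (50 and 100 mg; 15 mg).

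**The plan's own figures.** 450 × 1 = 450 mg/day and 45 × 2 = 90 mg/day. Both constants in section 19.1 are reproduced.

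**Fully adherent patient at reduced dose d throughout.** Section 19.1 score = 100 × d / full dose.

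| Drug | Assumed dose (mg/day) | Score | Below 80%? |
|---|---|---|---|
| LGX818 | 400 | 88.9% | no |
| LGX818 | 350 | 77.8% | yes |
| LGX818 | 300 | 66.7% | yes |
| MEK162 | 75 | 83.3% | no |
| MEK162 | 60 | 66.7% | yes |
| MEK162 | 45 | 50.0% | yes |

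Against the prescribed dose, every row would score 100%.

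**Share of exposure needed to fall below 80%.** With a share f of days at the reduced dose, score = 100 × [1 − f(1 − d/full)]. This is below 80% when f > 0.20 / (1 − d/full).

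- Two-thirds dose: 0.20 / 0.333 = 0.60.
- Half dose: 0.20 / 0.50 = 0.40.
- 350 mg of LGX818: 0.20 / 0.222 = 0.90.

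**Overlap with the cycle-count criterion.** Reductions lasting more than 3 consecutive cycles are already a major deviation. At two-thirds dose with cycles of equal length:

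- 2 reduced cycles of 3: (1 + 2 × 0.667) / 3 = 77.8%.
- 3 reduced cycles of 4: (1 + 3 × 0.667) / 4 = 75.0%.

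Both fall below 80% although the cycle-count criterion tolerates them. With only 2 or 3 reduced cycles at this dose, total oral exposure can be at most 3 or 4 cycles respectively for this to happen.

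Arm C's oral lead-in is 8 weeks, or 2 cycles, so the lead-in alone cannot trigger the cycle-count criterion. If those 56 days are the patient's only oral exposure and 34 of them are at two-thirds dose, the score is (22 + 34 × 0.667) / 56 = 79.8%.

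**Over-intake.** For a 300 mg LGX818 prescription, taking 450 mg/day is 150% of prescribed but scores 100%. Taking 130% of that prescription (390 mg/day) scores 86.7%. The formula passes 120% only above 540 mg/day, which is 540/300 = 180% of prescribed. For a patient prescribed full dose, intake above 540 or 108 mg/day is still flagged.

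**The case against.** The strongest objection is that the SAP never says that the section 19.1 percentage applies the section 6 rule. Section 19 gives it a descriptive role only. Exclusion also requires the non-compliance to be repeated or severe, and it passes through the Data Review Meeting and case-by-case agreement. Those reviewing the data would have Listing 42 and, in Listings 43 and 44, whether the drug was taken correctly and how many capsules came back. This stands, and the PP consequence is therefore conditional. It does not remove the mismatch: a numerical exclusion rule exists, one compliance percentage is derived, and its denominator is not the one that the rule names.

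A second objection is that the prescribed dose is undefined and may mean the protocol dose; the protocol is not among the documents shown. On that reading sections 6 and 19.1 agree. However, the 80% limit would then remove patients for short reductions that the separate criterion in section 6 tolerates, as the 2-of-3 and 3-of-4 cases show, so a clarification would still be needed.

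A reader might infer that adherent patients on a reduced dose are generally excluded and that overdosing is missed. The documents do not support this. Reductions to 400 mg of LGX818 or 75 mg/day of MEK162 stay above 80%; longer consecutive reductions are excluded anyway; and intake above 120% of full dose is caught. A reader might also infer a bias between arms, since oral exposure differs by arm. The documents give no frequency or depth of reductions, so no size can be put on that.

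**Conclusion.** The mismatch is real and worth correcting, with limited reach. That Table 24 measures relative dose intensity under a compliance label follows from section 19.1 as written. That the PP set would misclassify some patients holds only if the same percentage is used for the section 6 limits, which the SAP leaves unstated.

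Under that condition the affected patients are those with a dose below 80% of full for enough of their exposure, mainly with short oral exposure or non-consecutive reductions, and those who exceed a reduced prescription without passing 120% of full dose. The numerical illustrations rest on assumed dose levels.

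Only Table 24 and the PP repeat of OS can be affected. The primary and secondary analyses are in the ITT set and do not change.

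**What to change.** Reconcile sections 6 and 19.1 as follows.

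- In section 19.1, define compliance (%) = total dose taken / sum over cycles of (dose prescribed in that cycle × days) × 100, using the dose and reduced-dose fields shown in Listing 42.
- Before doing so, confirm that those fields hold the prescribed rather than the administered dose for every cycle. The listing shell does not say.
- State in section 6 that the 80-120% rule is applied to this quantity.
- Keep the present 450 mg and 90 mg formula as a separate row for each drug in Table 24, labelled relative dose intensity.

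The cost is a change of SAP wording, one extra derived variable and two extra rows in Table 24. If the listed fields do hold the prescribed dose, no new data are needed. The change concerns a derivation only and leaves every dosing rule as it is.

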20. EFFICACY OUTCOMES

20.1. PRIMARY EFFICACY

20.1.1. PRIMARY EFFICACY VARIABLE & DERIVATION

OS is the primary endpoint of the study. OS will be calculated from the date of randomization until the date of death from any cause. Any patient not known to have died at the time of data analysis will be censored at the time of the last recorded date on which the patient was known to be alive.

OS (months) = $[(\text{Date of death or last contact} - \text{date of randomization} + 1) / 30.4]$

20.1.2. ANALYSIS OF PRIMARY EFFICACY VARIABLE

The analysis will be performed in the ITT set and in the PP set.

The estimate of the survivor function using the Kaplan-Meier approach will be displayed graphically by treatment arm. Median time and the corresponding two-sided 95% confidence interval will be presented together with the estimates for the other quartiles (SAS procedure PROC LIFETEST) by treatment arm separately.

SAS-code for Kaplan-Meier approach[3]:

```
PROC LIFETEST DATA =  PLOTS=SURVIVAL(ATRISK(OUTSIDE(0.15)))
  OUTSURV= <output dataset> CONFTYPE=LOGLOG;
```

```
TIME <OS time in months>* <flag with censored data>(0)1;  

STRATA <treatment group>;  

RUN;
```

```
DATA <new dataset>;  

SET <output dataset>;  

UCL = ROUND(100*(1-SDF_UCL),.1);  

LCL = ROUND(100*(1-SDF_LCL),.1);  

RUN;
```

A Cox's proportional hazard regression model will also be performed to assess the influence of some baseline covariates on OS. Covariates of interest are those reported in section 9.1. Hazard ratios estimates with their 95% confidence limits will be also presented (SAS procedure PROC PHREG).

SAS-code for Cox's proportional hazard regression model [4,5]:

```
PROC PHREG DATA = <adam.dataset>;  

  CLASS <arm>(REF=FIRST) <gender>(REF=<'MALE'>) <melanoma type>(REF=FIRST) <stage of  

diagnosis>(REF=FIRST) <ECOG PS>(REF=FIRST) / PARAM=REF;  

  MODEL <duration of OS in months>*<censoring>(0) = <arm> <age> <gender> <melanoma type>  

<stage of diagnosis> <LDH level> <ECOG PS> / TIES=EFRON RISKLIMITS;  

RUN;
```

20.2. SECONDARY EFFICACY

The secondary analyses will be performed in the ITT set.

20.2.1. SECONDARY EFFICACY VARIABLES & DERIVATIONS

The secondary efficacy endpoints are:

- a) Total PFS, calculated from the date of randomization until the date of the second progression (i.e., the progression to second treatment); any progression or death will be considered as an event if patient cannot complete treatment sequence.
 Any patient not known to have experienced progression or died at the time of data analysis will be censored at the time of the last recorded date on which the patient was known to be alive without disease progression.
 Total PFS (months) = [(Date of second progression or any progression/death or last contact – date of randomization +1)/30.4]
- b) 3 years PFS rate (PFSR), calculated from the date of randomization until the date of progression or death from any cause. This rate estimates the proportion of patients who did not progress and were alive 3 years after randomization.
- c) Percentage of patients alive at 2 and 3 years;
- d) Best overall response rate (BORR), defined as the best response designation, as determined by the investigator, recorded between the date of randomization and the date of objectively documented progression per RECIST version 1.1 criteria;
- e) Duration of response (DoR), calculated as the time from the date of first documented response (CR or PR) until the date of the first documented progression or death due to

¹ where 0=censored; 1 = event.

underlying cancer. If a patient with a CR or PR has no progression or death due to underlying cancer, the patient is censored at the date of last adequate tumor assessment;

DoR (months) = $[(\text{Date of first documented progression/death due to underlying cancer or date of last tumor assessment} - \text{date of first CR or PR} + 1)/30.4]$

- f) Health-related quality of life (HRQoL), by means of the 30-item European Organisation for Research and Treatment of Cancer quality of life questionnaire (EORTC QLQ-C30);
- g) General health status, by means of the European Quality of Life 5-Dimensions (EQ-5D) questionnaire;
- h) Impairment of work productivity and activity, by means of the Work Productivity and Activity Impairment: General Health (WPAI:GH) questionnaire.

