4.3. DESCRIPTION OF TREATMENTS

The following IMPs will be used in the study:

- Arm A: Combo Target (LGX818 450 mg p.o. od + MEK162 45 mg p.o. bid) until PD; then Combo Immuno (nivolumab 1 mg/kg solution i.v.combined with ipilimumab 3 mg/kg solution i.v.every 3 weeks for 4 doses then nivolumab 3 mg/kg solution i.v.every 2 weeks) until PD.
- Arm B: Combo Immuno (nivolumab 1 mg/kg solution i.v.combined with ipilimumab 3 mg/kg solution i.v.every 3 weeks for 4 doses then nivolumab 3 mg/kg solution i.v.every 2 weeks) until PD; then Combo Target (LGX818 450 mg p.o. od + MEK162 45 mg p.o. bid) until PD.
- Arm C: Combo Target (LGX818 450 mg p.o. od + MEK162 45 mg p.o. bid) for 8 weeks followed by Combo Immuno (nivolumab 1 mg/kg solution i.v.combined with ipilimumab 3 mg/kg solution i.v.every 3 weeks for 4 doses then nivolumab 3 mg/kg solution i.v.every 2 weeks) until PD; then Combo Target (LGX818 450 mg p.o. od + MEK162 45 mg p.o. bid) until PD.

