Subjects will be assessed for response by computed tomography (CT) or Magnetic Resonance Imaging (MRI). All measurable and non-measurable lesions must be documented at screening (within 28 days prior to randomization) and re-assessed at each subsequent tumor evaluation (every 8 weeks (+/- 1 week) for the first year, every 12 weeks (+/- 1 week) while the patient is on study). Tumor assessments with CT or MRI scans of the brain, chest, abdomen, and pelvis will be performed until disease progression after the second combo treatment per RECIST v1.1.

For patients who discontinue study treatment for reason other than investigator-determined disease progression, tumor assessments should continue to be performed as scheduled.

Patients will continue to be on study and can be switched to the subsequent therapy after PD as per protocol in both arm A and B.

In case of an interruption of the treatment in arm C, reason other than investigator-determined disease progression, during the first 8 weeks (2 cycles of therapy), patient can continue the study treatment with combo immuno, as scheduled.

For patients with palpable/superficial lesions, clinical disease assessments by physical examination should be performed at baseline and throughout study treatment as clinically indicated. Color photographs with ruler/calipers will be taken at baseline and at all subsequent tumor assessment time points.

The National Cancer Institute Common Toxicity Criteria for Adverse Events (NCI CTC-AE) Version 4.03 will be used to evaluate the clinical safety of the treatment in this study. Patients will be assessed for AEs at each clinical visit and as necessary throughout the study.

Biomarker study

A correlative biological study will be performed for the evaluation of biomarkers on the biological sample available (paraffin-embedded tissue, frozen tissue, blood, serum, etc.). Approximately 80-90 patients will take part in the biomarker study.

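### Total PFS has an ambiguous event in Arm C and an incomplete, self-contradictory censoring rule in all arms, so comparability across arms is not assured

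*Supplement*

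**What the plan says.** **Event.** Total PFS runs "until the date of the second progression (i.e., the progression to second treatment". A fallback follows: "any progression or death will be considered as an event if patient cannot complete treatment sequence". The SAP does not define when a patient cannot complete the sequence.

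**Censoring text.** "Any patient not known to have experienced progression or died at the time of data analysis will be censored", at the "last recorded date on which the patient was known to be alive without disease progression".

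**Formula in the same item.** The end date is "Date of second progression or any progression/death or last contact". Listing 52 likewise has one column for second progression or last contact. The total PFS shell (Table 29 in the body of the shells, 27 in their contents list) repeats the event, the censoring text and the formula.

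**Arm C sequence.** Section 4.3: "Arm C: Combo Target (LGX818 450 mg p.o. od + MEK162 45 mg p.o. bid) for 8 weeks followed by Combo Immuno" until progression, then Combo Target again until progression. Table 1 in Section 8.1 gives Arm C three baselines, with Combo Immuno at Baseline 2. Arms A and B have two.

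**Imaging.** Section 4.4 says scans "will be performed until disease progression after the second combo treatment per RECIST v1.1". It describes the switch after progression for Arms A and B only.

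**Duration of response.** Item (e) says that if a responder "has no progression or death due to underlying cancer, the patient is censored at the date of last adequate tumor assessment". Item (b), the 3-year PFS rate, counts death from any cause.

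**The concern.** Total PFS is the first-listed secondary endpoint of a trial about treatment sequence. Section 20.2.2 reports it as Kaplan-Meier medians by arm and through a Cox model, and Section 9.1 puts arm among the covariates, so hazard ratios between arms will be printed. Two programmers following the SAP could date the Arm C event on different treatment periods. They could also treat patients who have progressed once and are still on the next treatment in different ways. At any data cut in a sequencing trial such patients are an ordinary group, not a rare exception.

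**Working it through.** **1. The plan's own figures.** The SAP states no figure for total PFS. Its OS design reproduces: 69 patients and at least 30 alive at 24 months, with 33% against 48%, give an exact one-sided alpha of 0.0446 and power of 0.808. Then 207/0.9 = 230. This point does not touch those numbers.

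**2. The event, arm by arm.**

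| Arm | Periods (4.3, 8.1) | Second progression falls on | Progression on the second period is |
|---|---|---|---|
| A | target, immuno | immuno | second progression |
| B | immuno, target | target | second progression |
| C, no progression in the lead-in | target for 8 weeks, immuno, target | re-introduced target | **first** progression |
| C, progression in the lead-in, then immuno | the same | immuno | second progression |

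The two halves of the definition agree for Arm C only if second treatment means the treatment given after the first progression. The SAP does not say that. Section 4.4 has the same ambiguity: counted by periods, scans would stop before Arm C's third period.

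**3. Censoring.** Take a patient with first progression at P1, last adequate scan at A, last contact at L (P1 < A < L), alive with no second progression.
- Eligibility in the censoring text: not covered, because a progression is known.
- Date in the censoring text: just before P1, the last progression-free date.
- Fallback, if the sequence is judged impossible to complete: event at P1.
- Formula and Listing 52: censored at L. Any time from A to L without imaging counts as free of second progression.

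These rules give different results for one patient, and nothing shown ranks them.

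**4. Illustrative size.** Inputs from Section 4.2: exponential PFS, medians of 10 months (target) and 9.5 months (immuno). Added assumptions: independent periods, no deaths, every patient switches, the same medians in later lines, and uniform follow-up over assumed windows.

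For the sum of the two periods, S(t) = [10·2^(−t/10) − 9.5·2^(−t/9.5)] / 0.5.
- S(23.6) = (1.9479 − 1.6979)/0.5 = 0.500, so the median is 23.6 months in Arms A and B.
- S(24) = (1.8946 − 1.6490)/0.5 = 0.491.

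Arm C: the lead-in is 56/30.4 = 1.84 months.
- Progression on Combo Immuno, none in the lead-in: 1.84 + 9.5 = 11.3 months.
- Second progression, none in the lead-in: 1.84 + 23.6 = 25.4 months.
- Chance of progression in the lead-in: 1 − 2^(−1.84/10) = 12%. Allowing for it, simulation gives 11.2 and 23.6 months.

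Arm A by simulation, Kaplan-Meier median in months:

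| Follow-up (months) | Between 1st and 2nd progression | Censored at last contact | Censored at last progression-free date | First progression as event |
|---|---|---|---|---|
| 12–36 | 29% | 23.6 | 20.1 | 15.2 |
| 24–36 | 25% | 23.6 | 21.0 | 17.5 |
| 24–48 | 20% | 23.6 | 21.7 | 18.9 |
| 30–54 | 15% | 23.6 | 22.3 | 20.3 |

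The last-contact column stays at 23.6 because the simulation observes progression right up to last contact. It does not measure the bias from follow-up for survival only, which the documents give no means to size.

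**The case against.** A reader might infer that total PFS is a different quantity in Arm C. The documents do not support that. Second progression is the main wording in the text, formula, shell and listing. Each arm has two points at which treatment runs until progression, and the fallback ties the endpoint to the whole sequence. If that wording governs, all three arms share one definition; they differ only if the parenthesis is taken literally for Arm C. The censoring text is the same in every arm, so it does not make the definitions differ either.

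A reader might also infer that patients on second-line treatment will be censored at their first failure. That is one reading; the formula points to another.

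The simulated sizes are open to a fair attack. Total PFS cannot exceed OS, yet the simulated median of 23.6 months exceeds the plan's alternative OS median of 23 months, and 49% at 24 months exceeds its 48%. The no-death and universal-switching assumptions cause this, and the follow-up windows are not in the documents.

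On imaging, the arm-specific schedules are in protocol tables that are not shown. The SAP plans Arm C data after Baseline 3, and Section 4.4 keeps scans going after a stop for reasons other than progression. That limits, but does not remove, unimaged follow-up.

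Finally, no decision rule uses total PFS, and Section 8.3 rules out comparative tests. All of this lowers the severity. None of it supplies the missing rule or reconciles the two censoring dates.

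**Conclusion.** The point holds as an ambiguity and an internal contradiction. The Arm C event can be read in two ways. In all arms the censoring rule omits patients alive after one progression, and its date conflicts with the formula and Listing 52. Comparability across arms is therefore not assured.

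Under the assumptions above, the Arm C readings differ by a factor of about two (11.2 to 11.3 against 23.6 to 25.4 months). The censoring readings in Arm A differ by 1.3 to 8.4 months (23.6 − 22.3 and 23.6 − 15.2). These figures show the order of size only and should not be quoted as expected results.

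Primary OS and its 30-patient rule are unaffected. Severity: should-fix.

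A lesser, separate point is that duration of response censors deaths not due to cancer while the PFS rate counts every death. Item (e) is clear in itself, but treating a toxic death as censoring can flatter the estimate.

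**What to change.** - **Event.** Delete or correct the parenthesis. For each arm, name the event as second progression counted from randomization, or death from any cause. In Arm C this normally falls on the re-introduced Combo Target. State how a progression during the 8-week lead-in is counted. Defining the event as progression on the last planned combination is less safe: for an Arm C patient who progresses in the lead-in and again on immuno, it would be the third progression.
- **Fallback.** Keep it, and define when a patient cannot complete the sequence and which date is then used.
- **Censoring.** Censor every patient without the event, including those after a first progression, at the last adequate tumour assessment. Replace last contact in the formula, the total PFS shell and Listing 52.
- **Section 4.4.** Reconcile its second-combination wording with Arm C's three periods and the protocol schedules.
- **Duration of response.** Count death from any cause as an event, or report that as a sensitivity analysis.
- **Section 4.6.** It reports no change from the protocol's analyses; record any that results.

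The cost is SAP wording, derivation code, and a check that Arm C third-period tumour assessments are captured. Some follow-up time is lost by censoring at the last scan, and duration of response may look slightly less favourable.
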